7 TRIAL TREATMENTS

The present study is a basic physiology study, which aims to elucidate mechanisms underlying muscle atrophy by studying muscle metabolism in conditions of pharmacologically altered substrate availability. Participants will be randomized to receive one of two drugs (Acipimox and Salbutamol) or a placebo, to be taken orally during the 2-day forearm immobilization period. Products will be prescribed by [name], after thorough checking for the listed in- and exclusion criteria (Section 6).

All products will be taken 4 times daily, with or after the three main meals (i.e. breakfast, lunch, dinner), and before bed.

Participants will be able to contact the CI 24/7, and [name] will be available for advice throughout the supplementation period.

The study products are described below:

Acipimox

The drug Acipimox is a nicotinic acid analogue that inhibits adipose tissue lipolysis, lowers intramuscular lipid metabolites, and improves insulin sensitivity. Acipimox will be given in 250 mg capsules, taken 4 times daily, as this dose has been shown to improve insulin sensitivity in type 2 diabetes patients within a few days [20].

Acipimox may cause some mild-moderate side effects in approximately 2 out-of 10 people. These side effects can include: skin rash; red 'flushed' skin; itching; sensations of hot skin. Less common effects include stomach pain and weakness.

Salbutamol

The drug Salbutamol is a β 2-adrenoceptor agonist commonly used as a bronchodilator in asthma. In addition, β 2-agonists have been shown to stimulate glycogenolysis and glycolytic flux [21], and exert a hypertrophic effect [22] by increasing muscle protein synthesis and decreasing proteolysis [23, 24]. Salbutamol will be given in 4 mg tablets, taken 4 times daily, as this dose has been shown to lead to a significant increase in lean mass in [22].

Salbutamol may cause mild-moderate side effects in approximately 1 out-of 10 people. These side effects can include fine tremor ('shaking', especially of the hands), headache, dizziness, and nausea. Less common side effects include arrhythmias, low blood pressure, and muscle pain.

Placebo

The placebo supplement will contain lactose, microcrystalline cellulose, pregelatinised starch, sodium starch glycolate, and magnesium stearate. These are inert substances widely used in many pill and tablet formulations, and are unlikely to cause toxicity when taken orally.

8 ADVERSE EVENT RECORDING AND REPORTING

8.1 Definitions

An Adverse Event (AE) is any unfavourable and unintended sign, symptom, syndrome or illness that develops or worsens during the period of observation in the study.

An AE does include a / an:

1. exacerbation of a pre-existing illness.
2. increase in frequency or intensity of a pre-existing episodic event or condition.
3. condition detected or diagnosed after medicinal product administration even though it may have been present prior to the start of the study.
4. continuous persistent disease or symptoms present at baseline that worsen following the start of the study.

An AE does not include a / an:

1. medical or surgical procedure (e.g., surgery, endoscopy, tooth extraction, transfusion); but the condition that leads to the procedure is an AE.
2. pre-existing disease or conditions present or detected at the start of the study that did not worsen.
3. situations where an untoward medical occurrence has not occurred (e.g., hospitalisations for cosmetic elective surgery, social and / or convenience admissions).
4. disease or disorder being studied or sign or symptom associated with the disease or disorder unless more severe than expected for the participant's condition.
5. overdose of concurrent medication without any signs or symptoms.

A Serious Adverse Event (SAE) is any adverse event occurring following study mandated procedures, having received the treatment or intervention that results in any of the following outcomes:

1. Death
2. A life-threatening adverse event
3. Inpatient hospitalisation or prolongation of existing hospitalisation
4. A disability / incapacity
5. A congenital anomaly in the offspring of a participant

Important medical events that may not result in death, be life-threatening, or require hospitalisation may be considered a serious adverse event when, based upon appropriate medical judgment, they may jeopardize the patient or participant and may require medical or surgical intervention to prevent one of the outcomes listed in this definition

All adverse events will be assessed for seriousness, expectedness and causality:

A distinction is drawn between serious and severe AEs. Severity is a measure of intensity whereas seriousness is defined using the criteria above. Hence, a severe AE need not necessarily be serious.

8.2 Recording and reporting of adverse events

Any adverse effects noted will be recorded in the adverse event log and reported to the CI and the study sponsors as per standard University of Exeter sponsor protocols (please refer to Letter from sponsor, included in this application). The CI will have a professional obligation to closely monitor participants and in the event of an adverse event being identified, follow established clinical treatment or referral protocols.

Participants will be instructed to contact the study team immediately should they feel unwell, and will be provided with contact numbers for contacting the team directly. Participants will be issued with a

card indicating their participation. This card will also identify their allocation code and identify reasons and who to contact should breaking the allocation code become necessary.

8.3 Emergency unblinding

The investigators may identify the treatment for each participant through sealed envelopes in the event of a medical emergency or SAE when treatment is dependent on knowledge of the actual drug received. The CI will be notified if the treatment code for a participant is broken, and the date and the reason(s) for breaking the blind will be noted in the CRF in a timely manner (notification of Sponsor immediately as practicable by phone or fax, followed by a written narrative of the event within 24 hours, as described above). Emergency unblinding will be carried out by the medical collaborator ([name]). He will at all times have access to the sealed list with participant names and treatment allocation.

9 STATISTICS AND DATA ANALYSIS

9.1 Sample size calculation

We have powered the study to detect a difference in forearm glucose uptake (primary outcome measure) between 1) Acipimox vs placebo, and 2) Salbutamol vs placebo. We have powered the study based on detecting differences in the change in forearm glucose uptake as measured during the hyperinsulinaemic-euglycaemic clamp, which is golden standard to measure insulin sensitivity. We have recently generated pilot data to demonstrate that forearm glucose uptake decreases by $13\pm 8\%$ (mean \pm SD) in response to mixed meal ingestion following 2 days of forearm immobilization. Based on our hypotheses, lowering lipid availability (via Acipimox) and stimulating glycolytic flux (via Salbutamol) will alleviate insulin resistance (i.e. prevent the decline in forearm glucose uptake). The following data were used to estimate the effect size, using $\alpha = 0.05$; power = 80%; significance = 5%:

- 1) Placebo ($-13\pm 8\%$) vs Acipimox ($0\pm 8\%$; preservation of forearm glucose uptake [14]. Effect size: 1.625. Required: $n=8$
- 2) Placebo ($-13\pm 8\%$) vs Salbutamol ($-4.3\pm 6\%$; 66% attenuation of decline in forearm glucose uptake by a beta2-agonist [28, 29]. Effect size: 1.23. Required: $n=12$

To have enough power for both comparisons, $n=12$ participants will be included in all groups (i.e. placebo, Acipimox, Salbutamol).

Thus, assuming a $\leq 20\%$ dropout rate (in our experience, similar immobilization studies do not exceed this drop-out rate when using healthy adults), we will recruit 45 healthy adults 18-40 years old, from both sexes, who will be split across 3 parallel groups (i.e. $n=15$ per group, ensuring completion of $n=12$ per group).

Sample size was calculated using G*Power 3.1.9.2.

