9.3.2 Primary outcome analysis

The primary outcome measure for this study is forearm glucose uptake, measured during the steady-state phase of a 3-h hyperinsulinaemic-euglycaemic-hyperaminoacidaemic clamp. A two-way ANOVA, with and treatment (placebo vs Acipimox vs Salbutamol) as between-subjects factor and time (pre vs post immobilization) as within-subjects factor. A Bonferroni post-hoc test will be used to locate individual differences.

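### The sample size tests each drug-placebo comparison at an unadjusted 5%, but the analysis applies Bonferroni; Salbutamol power at 12 completers per group is then about 73% or 66%, not 80%

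*Combined protocol and SAP*

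**What the plan says.** Section 9.1 powers the trial for two comparisons, "between 1) Acipimox vs placebo, and 2) Salbutamol vs placebo", based on "detecting differences in the change in forearm glucose uptake". The settings are "power = 80%; significance = 5"%. Each comparison is sized separately: Acipimox with an effect size of 1.625 and 8 per group, Salbutamol with 1.23 and 12 per group. The larger number is used in every group "To have enough power for both comparisons". Recruitment is 15 per group, so that 12 remain after up to 20% dropout. Multiple testing is not mentioned.

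Section 9.3.2 plans a two-way ANOVA with treatment (three groups) between subjects and "time (pre vs post immobilization) as within-subjects factor". It adds: "A Bonferroni post-hoc test will be used to locate individual differences". It does not say which comparisons are meant, how many there are, or whether they are contrasts of change.

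**The concern.** The test used for sizing is not the test planned for analysis. A Bonferroni correction lowers the significance level of each comparison, and so lowers power at a fixed sample size. The claim of adequate power for both comparisons has to hold at the level actually used, and 9.1 does not check it there.

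Two things are at stake. First, if Salbutamol does exactly what 9.1 assumes, the corrected test misses it more often than the plan states, so a null Salbutamol result would carry less evidence than the stated 80% suggests. Second, a three-by-two treatment by time layout allows several post-hoc families: two drug-placebo contrasts of change, three pairwise contrasts, pre-post tests within groups, or comparisons of cell means. With none chosen, the significance level for the primary comparisons stays open until analysis.

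**Working it through.** **Inputs (section 9.1).** Percentage change in forearm glucose uptake: placebo -13 (SD 8), Acipimox 0 (SD 8), Salbutamol -4.3 (SD 6). Alpha 0.05, target power 80%, 12 completers per group. Sidedness is not stated.

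**Effect sizes.** d = difference / sqrt((SD1² + SD2²)/2).
- Acipimox: 13/8 = 1.625.
- Salbutamol: (13 - 4.3)/sqrt((64 + 36)/2) = 8.7/7.07 = 1.23.

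**Reproducing the plan.** Two-sample t-test, noncentral t with df = 2n - 2 and noncentrality d·sqrt(n/2), two-sided 0.05.
- Acipimox: 79.7% at n = 7 and 85.6% at n = 8, so 8 per group.
- Salbutamol: 78.4% at n = 11 and 82.1% at n = 12, so 12 per group.
- Dropout: 12/(1 - 0.20) = 15 per group, 45 in all.

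One-sided tests would give 6 and 9, so the stated figures are two-sided at an unadjusted 5%.

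**Power under Bonferroni.** The family is an assumption, because 9.3.2 does not give one. Two contrasts give 0.05/2 = 0.025; three pairs give 0.05/3 = 0.0167. For Salbutamol at n = 12 the noncentrality is 1.23 × sqrt(6) = 3.01, with df = 22.

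| Comparison | n per group | 0.05 | 0.025 | 0.0167 |
|---|---|---|---|---|
| Salbutamol vs placebo | 12 | 82.1% | 72.5% | 66.4% |
| Salbutamol vs placebo | 15 | 90.2% | 83.5% | 78.9% |
| Acipimox vs placebo | 12 | 96.7% | 93.4% | 90.7% |

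Completers per group for 80% Salbutamol power: 12, 14 and 16 at the three levels. At 20% dropout the last two mean recruiting 14/0.8 = 17.5, so 18, or 16/0.8 = 20 per group.

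**Check with the planned ANOVA's error term.** In 400,000 simulated trials with 12 per group and the pooled three-group error (df = 33), Salbutamol power under Bonferroni is 71% (two contrasts) and 65% (three pairs). The treatment by time F test, which with two time points equals a one-way F test on change, has 96% power.

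**Holm on the two drug-placebo contrasts, n = 12 (simulation, separate two-group t-tests).**

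| Scenario | Salbutamol power |
|---|---|
| SDs as in 9.1, Acipimox works as assumed | 81% |
| SDs as in 9.1, Acipimox has no effect | 73% |
| SD 8 in all groups, Acipimox works as assumed | 71% |
| SD 8 in all groups, Acipimox has no effect | 61% |

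With the SDs of 9.1 and the pooled ANOVA error, the first two figures are 80% and 71%. With SD 8 in all groups d falls to 8.7/8 = 1.09, and Bonferroni gives 61% (two contrasts) or 54% (three pairs).

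**Familywise error with no true effects.** Testing the two contrasts uncorrected gives 9.1% without an F gate and 4.2% after a significant F test. Holm gives 4.7%.

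**The case against.** - **The family is assumed.** Neither 73% nor 66% can be read directly from the plan. This is fair: the certain defects are the unnamed family and the missing allowance, and the percentages show their size. Two contrasts is the better-supported reading, since 9.1 names exactly two. But any Bonferroni family that contains both gives 73% or less.
- **Fifteen per group are recruited.** If nobody drops out, two contrasts give 83.5%, and 14 completers per group already give 80.4%. This limits the shortfall without removing it. The plan's own completion target is 12, and three pairs stay just under 80% even at 15.
- **The F test is well powered.** At 96% it is, but a significant overall test does not show that Salbutamol differs from placebo, which is what 9.1 claims to power.
- **Holm is one choice among several.** With three groups, unadjusted contrasts after a significant F test also control familywise error. Salbutamol power is then about 81% if Acipimox works and 77% if it does not, against 81% and 73% for Holm. So Holm is not the most powerful option in every case. It is never less powerful than Bonferroni on the same two contrasts, and it does not depend on an omnibus test that includes a comparison 9.1 does not power.
- **The Salbutamol SD of 6% may be sourced.** It stands beside references 28 and 29, which may cover it. The main result takes 6% as given; 8% is only a sensitivity case.

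**Conclusion.** The concern holds. The arithmetic in 9.1 is right for the test it assumes, but that is not the test in 9.3.2. At 12 completers per group, with the effects and SDs of 9.1, Salbutamol power is 72.5% with two Bonferroni contrasts and 66.4% with three, against a planned 80% and 82.1% as sized. The chance of missing a Salbutamol effect of the assumed size rises from 18% to 27% or 34%. Acipimox is adequately powered throughout.

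These figures assume two-sided tests of between-group differences in percentage change. Pooling the error over three groups lowers the Salbutamol figures by one or two points. The point should be fixed; it affects one of the two powered comparisons and can be corrected by wording.

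**What to change.** **Section 9.3.2.** Replace the Bonferroni post-hoc test with two pre-specified contrasts of change, Acipimox vs placebo and Salbutamol vs placebo, tested by Holm at a familywise two-sided 5%. Label Acipimox vs Salbutamol exploratory. State whether the contrasts use separate two-group errors or the pooled ANOVA error.

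**Section 9.1.** Restate Salbutamol power under Holm at 12 per group as about 81% if Acipimox works as assumed and about 73% if it has no effect (80% and 71% with the pooled error). Add the sensitivity figures for a common SD of 8%, about 71% and 61%, and state the basis for the 6%.

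**If Bonferroni is kept.** Name the family and restate Salbutamol power as 73% (two contrasts) or 66% (three pairs). Alternatively, raise the completion target to 14 or 16 per group, which at 20% dropout means recruiting 54 or 60 participants instead of 45.

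**Cost.** The Holm route needs only wording in two sections and no extra participants. Acipimox vs Salbutamol loses confirmatory status, and Salbutamol reaches 80% only if Acipimox works as assumed, so both figures must be reported.

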9.2 Planned recruitment rate

The study will recruit 45 (taking into account a 20% dropout rate, see paragraph 10.1), young healthy males and females, primarily from the University student population. The planned recruitment rate is 2 participants per month over a 24 month period. Participants will be recruited at a single centre, and we foresee no issue capturing the eligibility criteria. We expect a screening failure rate not exceeding 50%, based on previous experience.

9.3 Statistical analysis plan

9.3.1 Summary of baseline data and flow of participants

Key baseline data will include anthropometric data (height, weight, BMI, fat mass), glucose and insulin concentrations, forearm glucose uptake, postabsorptive and postprandial muscle protein synthesis, forearm muscle volume, and forearm branched-chain amino acid (BCAA) and fatty acid balance. All baseline variables will be analysed using One-Way ANOVA to determine whether there are differences between groups.

A CONSORT flow diagram will be produced following completion of the study, and published in the manuscript(s) when possible.

9.3.2 Primary outcome analysis

The primary outcome measure for this study is forearm glucose uptake, measured during the steady-state phase of a 3-h hyperinsulinaemic-euglycaemic-hyperaminoacidaemic clamp. A two-way ANOVA, with and treatment (placebo vs Acipimox vs Salbutamol) as between-subjects factor and time (pre vs post immobilization) as within-subjects factor. A Bonferroni post-hoc test will be used to locate individual differences.

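### Section 9.1 powers the trial on percentage change in forearm glucose uptake, but the ANOVA in 9.3.2, as naturally read, compares absolute changes, so the stated 80% power does not describe the planned test

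*Combined protocol and SAP*

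**What the plan says.** Section 9.1 (Sample size calculation) states: "We have powered the study based on detecting differences in the change in forearm glucose uptake as measured during the hyperinsulinaemic-euglycaemic clamp". All of its inputs are percentages. Placebo is set at -13 (SD 8)%, from a pilot study. Acipimox is set at 0 (SD 8)%, giving "Effect size: 1.625. Required: $n=8". Salbutamol is set at -4.3 (SD 6)%, justified as "66% attenuation of decline in forearm glucose uptake by a beta2-agonist", with effect size 1.23 and 12 per group. Recruitment is 15 per group, to leave 12 after up to 20% dropout.

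Section 9.3.2 (Primary outcome analysis) specifies "A two-way ANOVA, with and treatment (placebo vs Acipimox vs Salbutamol) as between-subjects factor and time (pre vs post immobilization) as within-subjects factor", followed by a Bonferroni post-hoc test. The number of comparisons adjusted for is not stated. Sections 9.3.1 to 9.3.4 mention no log transformation, no percentage-change endpoint and no baseline covariate.

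**The concern.** A model with visit (pre, post) as a factor needs a value at each visit, and a percentage change has no pre value. With uptake entered as measured, the treatment-by-time test compares mean absolute changes between arms. The word raw does not appear in 9.3.2, but this is the natural reading.

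The two scales agree only under particular conditions. If each person loses a given percentage of their own uptake, the same percentage is a large absolute fall in someone with high uptake and a small one in someone with low uptake. Baseline spread then adds to the SD of the absolute change, and the 8% and 6% SDs in 9.1 leave that part out. Salbutamol sets the sample size and has only about 2 points of power above 80%, so it is the exposed comparison.

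An unstated scale also leaves raw, percentage and log analyses of the primary outcome open to choice after the results are seen.

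**Working it through.** **Inputs.** Means, SDs, alpha, power and 12 completers per group come from 9.1; the model and the Bonferroni step come from 9.3.2. The baseline CV of uptake, c, is not in the documents, so a range of 20 to 50% is assumed. Sidedness is not stated either; a two-sided test reproduces the plan's sample sizes and a one-sided test does not.

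**1. The plan's own figures** (two-sample t-test, two-sided 5%)

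- Acipimox: d = 13/8 = 1.625; power 85.6% at n = 8 and 96.7% at n = 12.
- Salbutamol: d = 8.7/√((8² + 6²)/2) = 8.7/7.071 = 1.230; power 82.1% at n = 12.

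Both stated sample sizes reproduce.

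**2. Absolute change, if the percentage change p is independent of baseline**

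With two visits, the treatment-by-time contrast is a comparison of mean changes. Write the baseline as B (mean 1, CV c) and the change as B·p. Then

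SD(B·p) = √[SD_p²(1 + c²) + c²·mean_p²].

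At c = 40%:

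- Placebo: √(64 × 1.16 + 0.16 × 169) = √101.28 = 10.06%.
- Salbutamol: √(36 × 1.16 + 0.16 × 18.49) = √44.72 = 6.69%.
- d = 8.7/√((101.28 + 44.72)/2) = 8.7/8.544 = 1.018; power 66.4%.

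The formula treats the absolute change as normal. The simulation (20,000 runs, lognormal baseline, three arms, pooled error on 33 df) allows for its skewness.

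| Baseline CV | SD placebo / Salbutamol | d | Power, formula | Power, simulated | n per group for 80% (formula) |
|---|---|---|---|---|---|
| 0% | 8.00 / 6.00 | 1.230 | 82.1% | 81% | 12 |
| 20% | 8.56 / 6.18 | 1.165 | 77.9% | 78% | 13 |
| 30% | 9.22 / 6.40 | 1.097 | 72.8% | 74% | 15 |
| 40% | 10.06 / 6.69 | 1.018 | 66.4% | 70% | 17 |
| 50% | 11.06 / 7.04 | 0.938 | 59.4% | 64% | 19 |

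By the formula, Salbutamol power passes below 80% at a CV of about 14%. Acipimox power is 95.3, 93.3, 90.1 and 85.7% at CV 20, 30, 40 and 50%, and 80.2% at 60%. Under this model a log analysis keeps Salbutamol at 83-84% at every CV.

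**3. The same figures under other response models**

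- Percentages relative to mean baseline, so that absolute change is unrelated to a person's own baseline: raw-scale Salbutamol power is about 81% at every CV, while log-scale power falls to about 80, 77, 71 and 64% at CV 20, 30, 40 and 50%.
- Absolute change independent of baseline, but calibrated so that within-person percentages still average -13 (SD 8)% and -4.3 (SD 6)%: raw-scale power rises to 86.3% at CV 20%, 90.9% at 30% and 99.3% at 50%.

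**4. Bonferroni step**

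With no baseline variation at all, Salbutamol power at n = 12 is 72.5% at 0.05/2 and 66.4% at 0.05/3. Combined with step 2 at CV 30%, the formula gives 61.4% or 54.7%. On logs, under the proportional model, the simulation gives about 74-75% or 68-69%.

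**The case against.** A reader might infer that the 80% power holds only if baseline uptake hardly varies between people. The documents do not support that. It requires the percentage fall to be independent of baseline, which they never state. Section 9.1 gives the pilot fall as a mean and SD in percent, without saying whether these are within-person percentages or changes relative to the mean. Under the second reading the raw ANOVA matches 9.1, and moving to logs would cause the very loss it was meant to prevent. The condition is not sufficient either, because the Bonferroni step takes Salbutamol below 80% with no baseline variation.

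Nor can one say that baseline spread must be large. The sample covers both sexes, ages 18-40 and BMI 18.5 to 30, which makes some spread plausible. But no CV is given, and the units of uptake, including any scaling to forearm volume, are not stated.

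The raw treatment-by-time test is also a conventional analysis, with no bias or type I error inflation shown. The loss is gradual: about 4 points at CV 20% and 8 to 9 at 30%. If all 15 recruited per group completed, 80% would hold to a CV of about 35%.

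These objections stand, and they limit the direction and size of the effect. They do not remove the mismatch: 9.1 reports power for percentages, and 9.3.2 does not say that percentages, or a scale equivalent to them, will be analysed. The three extra participants per group are reserved for dropout.

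**Conclusion.** The mismatch holds: on its natural reading, 9.3.2 tests a different quantity from the one powered in 9.1, so the 80% does not describe the planned test. Its effect on power is conditional. If the response is proportional to baseline, as the percentage inputs and the relative attenuation assumed for Salbutamol suggest, Salbutamol power at 12 completers per group lies between 78% and about 60% over the assumed CV range, before any multiplicity adjustment. Acipimox stays above 80% throughout that range. If the percentages are relative to mean baseline, the raw test loses nothing. The documents do not settle which model applies, so neither a definite loss of power nor a general superiority of the log scale can be claimed. Severity: should be fixed.

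**What to change.** Before unblinding, establish from the pilot data what the -13 (SD 8)% refers to, and pre-specify in 9.3.2 one analysis scale that matches 9.1.

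- **If the percentages are within-person:** analyse log steady-state uptake at both visits. Report each drug-placebo contrast as a ratio of post/pre ratios with 95% CI. The Salbutamol assumption corresponds to 0.957/0.87 = 1.10. This is a relative effect, distinct from the 8.7-point difference in percentage change, and should be labelled so.
- **If the raw ANOVA is kept:** restate the 9.1 power for absolute change, using the pilot SD of absolute change. The pilot was run after a mixed meal, so applying that SD to the clamp is an assumption to state.

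In either case, state how many comparisons the Bonferroni step covers and compute the restated power at that level. Changing the scale does not cure the loss from adjustment. Do not let the primary scale depend on the trial data; check from the pilot that uptake is positive before committing to logs.

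The cost is a few sentences in 9.1 and 9.3.2, with no new trial data. The small downside is that effects are reported as ratios, or that a less favourable power figure is stated.

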5.5 Trial procedures

Please refer to page 11 for trial flow chart and schematic of the metabolic test days. The trial procedures are described below:

Screening visit (visit 1):

- Firstly, participants will be asked to meet the investigator so that the study can be explained to them in detail, and it is clear what they can expect from the research team and what will be expected of them. Assuming they are happy with what has been discussed, they will then provide written consent. Subsequently, they will complete a medical screening questionnaire and have their height, weight, body composition (Bodpod), and blood pressure measured.
- Participant's caloric requirements will be calculated by estimating Resting Metabolic Rate via the Henry equation, and then multiplying this value by an activity factor derived from the International Physical Activity Questionnaire (IPAQ) questionnaire.
- Forearm volume will be measured via anthropometry.
- Participants will be asked for any allergies or intolerances to ensure they can eat everything they will receive as part of the standardized diet.
- Participants will be provided with a food diary to record their habitual dietary intake for 3 consecutive days, including 2 week days and 1 weekend day.

Baseline metabolic test day (visit 2):

- Approximately 1 week prior to casting, at 8 AM, participants will visit the Clinical Research Facility at the Royal Devon & Exeter NHS Foundation Trust in an overnight fasted state for a metabolic test day.
- The following cannulas will be inserted by a trained research nurse: 1) retrogradely into a deep antecubital vein (draining the muscle bed) of the non-immobilised arm, 2) retrogradely into a superficial dorsal hand vein of the to-be-immobilised hand, and 3) anterogradely into an antecubital vein in the elbow of the to-be-immobilised arm for infusion of insulin, glucose, amino acids, and stable isotope amino acids. The cannulated hand will be placed into a hand-warming unit (air temperature 55°C) to arterialize the venous drainage of the hand.
- After insertion of all cannulas, a primed, continuous stable isotope infusion of L-[ring-²H₅]-phenylalanine (prime: 0.5 mg·kg⁻¹, infusion 0.5 mg·kg⁻¹·h⁻¹) will be started with participants in a supine position. Using this tracer approach we will be able to calculate muscle protein synthesis and plasma leucine oxidation.

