9.3.3 Secondary outcome analysis

Secondary outcome measures include postabsorptive and postprandial muscle protein synthesis, and forearm branched-chain amino acid and fatty acid balance. These data will be analysed in the same way as the primary outcome described above.

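### The primary ANOVA treats the pre-treatment value as an outcome; adjusting for it instead is a near-free improvement, probably small on the plan's own SD

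*Combined protocol and SAP*

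**What the plan says.** Section 9.3.2 (Primary outcome analysis) specifies a two-way ANOVA of steady-state forearm glucose uptake, with the three treatments as the between-subjects factor and "time (pre vs post immobilization) as within-subjects factor". The follow-up is stated in one sentence: "A Bonferroni post-hoc test will be used to locate individual differences". Section 9.3.3 carries this model over to the secondary outcomes: "These data will be analysed in the same way as the primary outcome described above".

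Section 9.3.1 deals with baseline separately: "All baseline variables will be analysed using One-Way ANOVA to determine whether there are differences between groups". It attaches no action to the result. No baseline covariate appears anywhere in the plan.

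Section 5.5 places the baseline test day at visit 2: "Approximately 1 week prior to casting, at 8 AM, participants will visit the Clinical Research Facility". The first dose is taken at visit 3, so the baseline value cannot be affected by treatment.

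Section 9.1 states the quantity that was powered: "We have powered the study based on detecting differences in the change in forearm glucose uptake".

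**The concern.** A measurement taken before treatment carries no information about the drug effect, but it does predict the later measurement. Its natural place is on the right-hand side of the model. Entering it as a second response has two consequences for the treatment-by-time contrast.

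- The slope of post on baseline is fixed at 1 instead of being estimated, so measurement error in the baseline passes into the result.
- A group that starts high by chance tends to show a larger fall. That regression to the mean stays in the drug-placebo estimate.

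With 12 completers per group, chance differences at baseline will not be negligible in baseline SD units, and any spare precision is worth having. The One-Way ANOVA tests in 9.3.1 do not help. If allocation is random, a baseline difference is due to chance whatever its p-value, and the p-value does not show how far that difference moves the primary estimate.

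**Working it through.** **Inputs.** From 9.1: Placebo change -13 (SD 8), Acipimox 0 (SD 8), Salbutamol -4.3 (SD 6), all in percent; alpha 0.05; power 80%; 12 completers per group. Not in the documents: the pre-post correlation rho and the between-subject CV of forearm glucose uptake. Both are assumptions below. Percent changes are treated as percentages of the baseline mean, with equal pre and post variances.

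**1. The plan's own figures.** These come from a two-sample t-test on change, two-sided, with noncentral t.
- Acipimox: d = 13/8 = 1.625, n = 8 per group, power 85.6%.
- Salbutamol: pooled SD = sqrt((8² + 6²)/2) = 7.07; d = 8.7/7.07 = 1.23; n = 12 per group, power 82.1%.

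Both sample sizes reproduce. They rest on change scores, which is what the treatment-by-time contrast compares.

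**2. What a chance baseline difference does.** Let D be the baseline difference between two arms and delta the true effect. The expected post difference is delta + rho·D. Subtracting baseline gives delta + rho·D - D = delta - (1-rho)·D. With baseline as covariate the D term vanishes.

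**3. Precision.** Let S be the common SD at each visit. The change score has variance 2·S²·(1-rho). After adjustment the residual variance is S²·(1-rho²). The ratio is (1+rho)/2.

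**4. What the plan's SD implies for rho.** From 8² = 2·CV²·(1-rho), rho = 1 - 64/(2·CV²). The SD of D is CV·sqrt(2/12) = 0.41·CV. The last column of the table is (1-rho) times that.

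| Assumed CV | rho | Variance gain | Salbutamol power, adjusted | SD of residual imbalance (points) |
|---|---|---|---|---|
| 20% | 0.92 | 4% | 83.5% | 0.65 |
| 30% | 0.96 | 2% | 82.6% | 0.44 |
| 40% | 0.98 | 1% | 82.3% | 0.33 |

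Adjusted power uses d = 1.23/sqrt((1+rho)/2) with 21 df, against 82.1% for change scores with 22 df. For scale, the standard error of the Salbutamol contrast is sqrt((64+36)/12) = 2.9 points and that of the Acipimox contrast is 8·sqrt(2/12) = 3.3 points. The planned effects are 8.7 and 13 points.

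The table counts the lost degree of freedom but not the small cost of estimating the slope. A three-arm calculation at rho 0.95 gives 83.0% adjusted against 83.3% for change. Towards the top of this range the precision gain is effectively nil.

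**5. If rho is lower.** Keeping d = 1.23 on the change scale, rho 0.7 gives a variance gain of 15% and power 88%. Rho 0.5 gives 25% and 91%. The gain can also be written SD²/(4·CV²). If the clamp SD of change were 16% with CV 30%, it would be 256/3600 = 7%; with SD 20% and CV 20%, it would be 400/1600 = 25%.

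**6. The baseline tests.** Suppose two arms of 12 differ at baseline by 0.5 SD, with the third midway. The between-group mean square is 12·(0.25² + 0.25²)/2 = 0.75 times the within-group variance. F is then below 1, so the test is silent. A pairwise gap of more than 0.5 SD arises by chance with probability 0.22.

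**The case against.** The strongest case for the plan is that nothing in it is wrong. A change-score comparison already subtracts each participant's baseline, is unbiased over randomisations, and is what 9.1 powered. The only figure in the documents that bears on the gain, the 8% SD of change, points to a high rho and a small benefit. A rho of 0.5 with that SD would need a baseline CV of only 8%, which nothing in the documents supports for a sample of both sexes aged 18-40 with BMI 18.5-30. All of this stands.

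Two things temper it. The 8% comes from pilot data after mixed-meal ingestion, not from the clamp used for the primary outcome, and visit 3 may follow visit 2 by 7 to 28 days. The clamp correlation could therefore be lower. Adjustment also removes the dependence on D at every rho.

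A reader might infer several stronger things that the documents do not support.
- That the primary analysis is biased or invalid: under the interaction contrast it is neither.
- That baseline is ignored apart from the significance tests: the interaction uses it. Section 9.3.2 does not name the contrast for the post-hoc test, but 9.1 speaks of change.
- That baseline is measured before randomisation: 5.6 gives no time of allocation, and only pre-treatment is documented.
- That the 9.3.1 tests will drive unplanned adjustment: no action is attached to them.

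**Conclusion.** The point holds as an optional, near-free improvement, not as an error. The planned treatment-by-time contrast is valid and consistent with the sample size. It is open to chance baseline differences by a factor of (1-rho), and it has error variance higher than a baseline-adjusted analysis unless rho is close to 1.

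On the plan's 8% SD of change and an assumed CV of 20-40%, both effects are small. The variance gain is 1-4%, Salbutamol power is 82-84% instead of 82%, and the residual imbalance has an SD of about 0.3-0.7 points against a standard error of about 3. Only if the clamp correlation were as low as 0.5-0.7 would the gain be material, at 15-25% of variance and power of 88-91%. These figures assume equal pre and post variances and a rho that the documents do not give. The baseline tests in 9.3.1 are a minor reporting matter.

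**What to change.** In 9.3.2, replace the two-way ANOVA by a linear model of post-immobilisation steady-state forearm glucose uptake on treatment (three levels), with the visit 2 value as covariate. Name the Acipimox-placebo and Salbutamol-placebo adjusted differences as the primary contrasts and report each with a 95% CI. Use the same form in 9.3.3, with each outcome's own visit 2 value. Settle the wording before unblinding.

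In 9.3.1, delete the One-Way ANOVA tests and give means and SDs by group.

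The cost is wording in three subsections and one error degree of freedom. No new data, visits or participants are needed, and the sample size in 9.1 can stay as it is.
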